9.3.2 Pharmacokinetic Statistical Methodology

PK parameters will be evaluated to determine the impact of topiramate co-administration on the PK of a single dose of lasmiditan and its metabolites. Log-transformed C_{max} , $AUC(0-\infty)$, and $AUC(0-t_{last})$ parameters will be evaluated in a linear mixed-effects model with fixed effects for treatment and a random effect for subject. The treatment differences will be back-transformed to present the ratios of geometric means and the corresponding 90% confidence interval (CI). The comparison of interest is:

Lasmiditan co-administered with topiramate (Day 14; test treatment) versus Lasmiditan alone (Day 1; reference treatment)

An example of the SAS code that will be used is as follows:

```
proc mixed data=xxx;
  class trtmnt subject;
  model l_pk = trtmnt / alpha=0.1;
  random subject;
  lsmeans trtmnt / pdiff;
run;
```

where l_pk is the log-transformed (base e) PK parameter.

A similar analysis will be performed to determine the impact of co-administration of a single dose of lasmiditan on the steady-state PK of topiramate. This analysis shall evaluate the log-transformed C_{max} and AUC_{τ} using a similar model to the one described above. The comparison of interest will be:

Topiramate co-administered with lasmiditan (Day 14; test treatment) versus Topiramate alone (Day 13; reference treatment)

The t_{max} will be analyzed using the Wilcoxon signed rank test. Estimates of the median difference based on the observed medians, 90% CIs and p-values from the Wilcoxon test will be calculated.

Additional analyses may be performed, as warranted.

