10.3.2.2. Pharmacokinetic Statistical Inference

Pharmacokinetic parameters will be evaluated to determine the impact of topiramate co-administration on the PK of a single dose of lasmiditan and its metabolites. Log-transformed C_{max} and AUC parameters will be evaluated in a linear mixed-effects model with fixed effects for treatment (lasmiditan co-administered with topiramate [Day 14; test treatment] versus lasmiditan alone [Day 1; reference treatment]), and a random effect for subject. The treatment differences will be back-transformed to present the ratios of geometric means and the corresponding 90% confidence interval (CI).

A similar analysis will be performed to determine the impact of co-administration of a single dose of lasmiditan on the steady-state PK of topiramate. The model will include the following treatments: topiramate co-administered with lasmiditan (Day 14; test treatment) versus topiramate alone (Day 13; reference treatment).

The t_{max} will be analyzed using the Wilcoxon signed rank test. Estimates of the median difference based on the observed medians, 90% CIs, and p-values from the Wilcoxon test will be calculated.

Additional analyses may be performed, as warranted.

11. References

Manitpisitkul P, Curtin CR, Shalayda K, Wang S, Ford L, Heald D. Pharmacokinetic interactions between topiramate and diltiazem, hydrochlorothiazide, or propranolol. *Clin Pharmacol Drug Dev*. 2014a;3(5):378-387.

Manitpisitkul P, Curtin CR, Shalayda K, Wang S, Ford L, Heald D. Pharmacokinetic interactions between topiramate and pioglitazone and metformin. *Epilepsy Res*. 2014b;108(9):1519-1532.

Posner K. State of the science: measurement of suicidal adverse events and the Columbia suicide severity rating scale. Boca Raton, FL: NCDEU; 2007.

Posner K, Melvin GA, Stanley B, Oquendo MA, Gould M. Factors in the assessment of suicidality in youth. *CNS Spectr*. 2007a;12(2):156-162.

Posner K, Oquendo MA, Gould M, Stanley B, Davies M. Columbia Classification Algorithm of Suicide Assessment (C-CASA): classification of suicidal events in the FDA's pediatric suicidal risk analysis of antidepressants. *Am J Psychiatry*. 2007b;165(7):1035-1043.

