6. TREATMENTS

The following is a list of the study treatment abbreviations that will be used in the TFLs.

Study Treatment Name	Treatment order in TFL
Placebo	1
200 mg lasmiditan	2
25 mg topiramate QD	3
25 mg topiramate BID	4
50 mg topiramate BID	5
50 mg topiramate + placebo	6
50 mg topiramate + 200 mg lasmiditan	7

D = Day; QD = once daily; BID = twice daily

The following treatment sequences may be displayed across some outputs.

Sequence	Treatment Sequence Description
1	Placebo / 25 mg topiramate QD / 25 mg topiramate BID / 25 mg topiramate BID / 50 mg topiramate BID / 50 mg topiramate + placebo
2	200 mg lasmiditan / 25 mg topiramate QD / 25 mg topiramate BID / 25 mg topiramate BID / 50 mg topiramate BID / 50 mg topiramate + 200 mg lasmiditan

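### Does the example PROC MIXED code in SAP 9.3.2 put the promised 90% confidence interval at risk?

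*SAP*

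**What the plan says.** The text of SAP 9.3.2 states the output required: "The treatment differences will be back-transformed to present the ratios of geometric means and the corresponding 90% confidence interval (CI". Protocol 10.3.2.2 sets the same target: "back-transformed to present the ratios of geometric means and the corresponding 90% confidence interval (CI". SAP 9.3.2 also names both contrasts and their direction: "Lasmiditan co-administered with topiramate (Day 14; test treatment) versus Lasmiditan alone (Day 1; reference treatment", and "Topiramate co-administered with lasmiditan (Day 14; test treatment) versus Topiramate alone (Day 13; reference treatment".

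A short code block follows the first contrast, introduced by "An example of the SAS code that will be used is as follows". Two of its lines matter here. The level is set in "model l_pk = trtmnt / alpha=0.1", and the treatment comparison is requested by "lsmeans trtmnt / pdiff". The block contains no ESTIMATE statement. The topiramate analysis is to use a similar model.

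SAP 6 lists the treatment names for the tables with a column headed "Treatment order in TFL". SAP 7 says the sample size does not rest on hypothesis testing. SAP 3 places the detailed output specification in a separate shell document, which is not among the public files.

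**The concern.** The text and the code in one section do not agree. In PROC MIXED, ALPHA= on MODEL sets the level for intervals on the fixed-effect parameter estimates. It does not pass to LSMEANS. PDIFF without CL prints the difference, standard error, degrees of freedom, t and p, but no limits. The block therefore stops short of the one inferential result that the section promises, and it serves as a pattern for lasmiditan, its metabolites and topiramate.

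Two further worries follow. A programmer who sees the gap might add CL alone. LSMEANS would then use its default 95% level, while the 0.1 elsewhere in the code suggests 90%. Also, default PDIFF subtracts the later treatment level from the earlier one, so the ratio could come out as reference over test if the treatment variable followed the table order in SAP 6. At stake would be a missing, mislabelled or inverted interval for the secondary pharmacokinetic objectives.

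**Working it through.** **1. Intended level.** The code has alpha = 0.1, and 1 − 0.1 = 0.90. The level the author had in mind agrees with the text.

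**2. Text and code side by side.**

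| Element | Text of SAP 9.3.2 | Example code |
|---|---|---|
| Fixed effect | Treatment | Treatment |
| Random effect | Subject | Subject |
| Response | Log-transformed parameter | Log-transformed parameter, derived beforehand |
| Contrast | Test against reference, named for each drug | Default pairwise difference |
| Level | 90% | 0.1, on MODEL only |
| Limits | Required | Not requested |
| Back-transformation | Required | Absent |
| Dataset | Not applicable | Placeholder name |

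The code matches the text on the model. It leaves out several output steps, and the limits are one of them. The exponentiation is missing too, and nobody would read that as a plan to report log differences.

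**3. Is information lost?** With complete pairs in the lasmiditan arm, the treatment degrees of freedom are 2n − (n + 1) = n − 1. SAP 7 gives about 30 enrolled, at least 21 completers and 2:1 allocation.

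- 30 × 2/3 = 20 pairs, so 19 df.
- 21 × 2/3 = 14 pairs, so 13 df. This assumes that completers keep the 2:1 split, which the SAP does not state.

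The 90% limits are exp(estimate ± t × SE), with t(0.95) = 1.729 at 19 df and 1.771 at 13 df. Estimate, SE and df are all printed, so the promised interval is recovered exactly. A simulated data set of 20 complete pairs confirmed that the mixed model gives the paired analysis: difference 0.0259 and SE 0.0644 both ways.

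**4. Size of the hypothetical mistake.** If CL were added without a level, t(0.975) would apply.

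- 19 df: 2.0930 / 1.7291 = 1.210, so 21.0% wider on the log scale.
- 13 df: 2.1604 / 1.7709 = 1.220, so 22.0% wider.

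As an illustration, take 20 pairs, a ratio of 1.00 and an assumed within-subject CV of 25%. The documents give only between-subject CVs. Then SE = √ln(1 + 0.25²) × √(2/20) = 0.0779. The 90% interval is 0.874 to 1.144, and the 95% interval is 0.850 to 1.177. Over assumed CVs from 15% to 30%, the 90% interval goes from 0.922–1.085 to 0.852–1.174, and the 95% interval from 0.906–1.104 to 0.823–1.215.

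These widths describe a mistake that the plan does not contain. It would take someone adding CL, leaving out the level, and labelling the result 90% against the text.

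**5. Direction.** In the SAP 6 table order, lasmiditan alone is 2, topiramate 50 mg twice daily is 5, and the combination is 7. Default differences would then be 2 − 7 and 5 − 7, both reference minus test. But SAP 6 lists display names in table order and does not say how the analysis variable is coded. An inversion is therefore conjecture. SAP 9.3.2 names test and reference for each contrast, and the geometric means required by SAP 9.1 would expose a reversed ratio.

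**The case for a change.** The strongest contrary case is that the block is offered as a sample of code that will actually be run and is the only template for several analytes. SAP 3 also says the SAP supersedes the protocol's statistical considerations. The 90% interval is the main inferential output for the secondary objectives, the correction is trivial, and the easiest patch gives the wrong level while looking right.

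Part of this stands. The mismatch is real: the option placement can be read directly from the SAP, and the block as printed would not output the interval. The rest does not carry. The precedence rule in SAP 3 is no help, because the SAP's own text, not only the protocol's, requires 90%. Calling the block an example matters, since it has a placeholder dataset and no back-transformation and so cannot be the full program. A missing interval is visible at once, and the programmer who fills it has the level in the same section. The wrong-level patch is possible, but it is a fault in programming that contradicts the plan, and checking the output against the stated 90% would catch it.

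**Conclusion.** The concern identifies a clerical slip in illustrative code and does not call for a change to the plan. The model, contrasts, direction and 90% level are all fixed in the text, and the effect on any planned result is nil: the geometric mean ratio and its 90% interval are the same with or without a tidier example. The 21% to 22% widening and the reversed ratio each depend on something the documents do not contain, namely a later programming error and an assumed treatment coding. The consequence is limited further because the study is not powered for hypothesis testing and no equivalence margin or decision rule uses the interval.

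This rests on two assumptions. The first is standard PROC MIXED option behaviour, which is software knowledge and was not tested in SAS. If LSMEANS did inherit the level and print limits, the mismatch would disappear and the conclusion would be the same. The second is that analysts follow the SAP text where the example is silent, which is the ordinary reading of an example.

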Lasmiditan and Metabolite PK Samples			Predose, 0.5, 1, 1.5, 2, 3, 4, 6, 8, 12 h	24, 36 h	48 h											Predose, 0.5, 1, 1.5, 2, 2.5, 3, 4, 6, 8, 12 h	24, 36 h	48 h		
Topiramate PK Samples															Predose, 0.5, 1, 1.5, 2, 3, 4, 6, 8, 12 h	Predose, 0.5, 1, 1.5, 2, 3, 4, 6, 8, 12 h			Time points at morning dose only.	
Genetic Sample		X																		

Abbreviations: BID = twice daily; BP = blood pressure; CRU = clinical research unit; C-SSRS = Columbia Suicide Severity Rating Scale; ECG = electrocardiogram; ED = early discontinuation; h = hour; min = minutes; PK = pharmacokinetics; QD = once daily.

Note: if multiple procedures take place at the same time point, the following order of the procedure should be used: ECG, vital signs, and venipuncture.

3. Introduction

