7. SAMPLE SIZE JUSTIFICATION

Approximately 30 subjects will be enrolled, so that at least 21 subjects complete the study. Subjects will be randomized in a 2:1 ratio of lasmiditan 200 mg : placebo. The sample size is customary for Phase 1 studies evaluating safety and tolerability, and is not powered on the basis of statistical hypothesis testing.

Subjects who are randomized but who do not complete Day 14 treatment may be replaced to ensure that enough subjects complete the study.

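### The tmax point estimate rests on the observed medians beside a paired signed rank test; if it is the difference of the two day medians, it does not match its own interval

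*SAP*

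**What the plan says.** SAP 9.3.2 names a paired test: "The t_{max} will be analyzed using the Wilcoxon signed rank test". The next sentence covers estimation: "Estimates of the median difference based on the observed medians, 90% CIs and p-values from the Wilcoxon test will be calculated". Protocol 10.3.2.2 has the same sentence apart from a comma: "Estimates of the median difference based on the observed medians, 90% CIs, and p-values from the Wilcoxon test will be calculated". The two documents therefore agree with each other.

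Neither document says:

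- whether the median difference is the difference between the two day medians or the median of the within-subject differences;
- how the 90% CI is obtained, since the closing reference to the Wilcoxon test may cover the CIs and p-values or the p-values alone;
- how ties and zero differences are handled.

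The comparisons are Day 14 against Day 1 for lasmiditan and its metabolites, and Day 14 against Day 13 for topiramate. tmax is a secondary endpoint for lasmiditan and topiramate and an exploratory one for the metabolites (protocol Table LAHT.1). On size, SAP 7 says "Approximately 30 subjects will be enrolled, so that at least 21 subjects complete the study" and "Subjects will be randomized in a 2:1 ratio of lasmiditan 200 mg : placebo", and adds that the sample size "is not powered on the basis of statistical hypothesis testing".

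**The concern.** The signed rank test works on each subject's own difference. Inverting it gives a confidence interval for the pseudo-median of those differences. The point estimate that belongs to that interval is the Hodges-Lehmann estimate, the median of all pairwise (Walsh) averages of the differences.

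The phrase about observed medians most naturally suggests something else: the Day 14 median minus the reference-day median. That statistic does not use the pairing, although protocol 5.4 justifies the design by within-subject comparison. It is also coarse, because tmax clusters at sampling times 0.5 to 1 h apart in the region where lasmiditan is expected to peak (1 to 2.5 h, protocol 3.2).

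What is at stake is a results table that contradicts itself. The printed shift can lie outside the interval beside it, or read 0.0 h next to a small p-value.

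**Working it through.** The plan states no tmax effect, SD or precision target, so it has no figure to reproduce.

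**Inputs from the documents**

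- Lasmiditan pairs under 2:1 allocation: 21 × 2/3 = 14 if only the minimum complete, and 30 × 2/3 = 20 if all complete.
- Lasmiditan sampling times up to 12 h (protocol section 2): Day 1 "Predose, 0.5, 1, 1.5, 2, 3, 4, 6, 8, 12 h"; Day 14 "Predose, 0.5, 1, 1.5, 2, 2.5, 3, 4, 6, 8, 12 h". Only Day 14 has a 2.5 h sample.

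**Assumed, not in the documents:** lognormal tmax with median 1.8 h; log-SD 0.25 or 0.40 between subjects and 0.20, 0.30 or 0.45 within; true shift 0 or 0.5 h; values set to the nearest scheduled time.

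**Step 1. Interval and matching estimate.** Let d be Day 14 minus Day 1 tmax. There are n(n+1)/2 Walsh averages (d_i + d_j)/2 with i ≤ j. The Hodges-Lehmann estimate is their median. Ignoring ties, the exact signed rank null distribution gives:

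- n = 14: 14 × 15/2 = 105 averages; CI from the 26th smallest to the 26th largest; coverage 90.9%.
- n = 20: 20 × 21/2 = 210 averages; CI from the 61st smallest to the 61st largest; coverage 90.3%.

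Neither the interval nor the p-value uses the reported point estimate, so changing that estimate leaves both alone.

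**Step 2. How often the estimate leaves its interval.** 5,000 simulated trials per scenario. Each row spans both between-subject SDs and both shifts.

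| Pairs | Within-subject log-SD | Difference of day medians outside the 90% CI | SD, difference of day medians (h) | SD, Hodges-Lehmann (h) | SD ratio |
|---|---|---|---|---|---|
| 14 | 0.20 | 6.4–8.7% | 0.26–0.27 | 0.17–0.18 | 1.51–1.58 |
| 14 | 0.30 | 3.0–4.9% | 0.31–0.33 | 0.23–0.25 | 1.30–1.38 |
| 14 | 0.45 | 1.3–2.5% | 0.41–0.44 | 0.34–0.36 | 1.17–1.26 |
| 20 | 0.20 | 12.6–14.3% | 0.25–0.27 | 0.14–0.15 | 1.67–1.90 |
| 20 | 0.30 | 5.8–7.9% | 0.29–0.30 | 0.20 | 1.46–1.49 |
| 20 | 0.45 | 2.2–3.4% | 0.35–0.38 | 0.29–0.30 | 1.23–1.27 |

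Separate runs of this kind differ by about a percentage point at the ends, so I summarise as roughly 2% to 13%, with an SD ratio of about 1.2 to 1.8. A wider set of assumptions (both log-SDs 0.2 to 0.5, median 1.75 h) gave 0.8% to 15.3% and ratios of 1.13 to 2.03. The Hodges-Lehmann estimate was never outside. Nor was the median of the paired differences, whose SD was 0.77 to 1.21 times that of Hodges-Lehmann in the runs tabulated here.

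**Step 3. A constructed example with n = 14.**

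- Day 1: 1, 1, 1.5, 1.5, 1.5, 2, 2, 2, 2, 2, 3, 3, 3, 4 h.
- Day 14, same subjects: 2, 1.5, 2, 2, 2, 2, 2, 1.5, 2, 2.5, 3, 4, 4, 4 h.

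Both day medians are 2.0 h, so their difference is 0.0 h. The differences comprise five zeros, one of −0.5, five of +0.5 and three of +1. Their median is 0.5 h, the Hodges-Lehmann estimate is 0.25 h, and the Walsh-average interval is 0.0 to 0.5 h.

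With zeros dropped, the six differences of size 0.5 share rank 3.5 and the three of size 1 share rank 8. The negative rank sum is 3.5 and the positive one is 5 × 3.5 + 3 × 8 = 41.5. The two-sided p-value is 0.02 by the normal approximation, or 2 × 7/512 = 0.027 by exact enumeration. A reported shift of 0.0 h would stand beside that p-value.

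The interval also just touches zero, because it keeps the zero differences while the test drops them. That is why a rule for ties and zeros is needed.

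**The case against.** **The sentence may not mean this.** It also permits the median of the paired differences, which never left the interval in the simulations and is about as precise as Hodges-Lehmann. It can also be read with only the p-values coming from the Wilcoxon test, in which case no CI method is specified. SAP 3 places output detail in TFL shells that are not available here. This stands: the mismatch is conditional on one reading. The sentence still needs rewriting, because two programmers could follow it and report different numbers.

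**Actual times are used, not nominal ones.** SAP 9.3.1 derives individual parameters from actual sampling times, and SAP 13.1 reports tmax as received. This does not rescue the estimate. Actual times still cluster around the schedule, and adding random deviations of up to 2 minutes either way (my assumption) raised the proportion outside the interval to between 2.6% and 20.5%.

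**Precision.** A reader might infer that the analysis loses precision or power. It does not: the interval and the p-value are the same whichever estimate is printed, and the study is not powered on tmax. Only the point estimate is noisier.

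**Both drugs.** A reader might carry the percentages over to topiramate. The ambiguous wording applies there too, but only a lasmiditan-like tmax was simulated. Topiramate has identical Day 13 and Day 14 sampling times, so the sizes do not transfer.

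**Consequence.** The primary objective is safety, no limit or decision rule is attached to tmax, and the Cmax and AUC ratios are untouched. This stands and sets the priority.

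**Conclusion.** The point holds, conditionally and at minor priority. On the natural reading, the tmax estimate and its signed rank interval target different quantities. The estimate then falls outside its own 90% CI in roughly 2% to 13% of trials and has about 1.2 to 1.8 times the SD of the Hodges-Lehmann estimate. These sizes rest on assumed lasmiditan variability and on 14 to 20 pairs. They are largest when within-subject variability is low.

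The documents do not support a claim that the inference is wrong or weakened, nor that the sponsor has definitely chosen the mismatched estimate. What they show is an underspecified sentence whose most likely implementation can print an estimate at odds with its interval or p-value.

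**What to change.** Replace the estimation sentence in SAP 9.3.2 with:

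> The Hodges-Lehmann estimate of the within-subject tmax difference (test minus reference), with its 90% CI from inverting the Wilcoxon signed rank test and the p-value from the same test, will be presented, with a stated rule for ties and zero differences; observed medians per treatment will be shown descriptively.

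The rule itself must be written in. In the simulations on scheduled times, 17% to 40% of pairs had a zero difference, so it will matter. Because the method departs from the protocol's wording, SAP 11 should list it as a change. The same section should acknowledge that lasmiditan has a 2.5 h sample on Day 14 but not on Day 1, which affects any estimator of the shift.

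The cost is a sentence of text and a few lines of code, with no new data. The CI and p-value stay as they are if the Wilcoxon CI was already intended. The downside is a change of target: Hodges-Lehmann estimates the pseudo-median, which equals the median difference only when the differences are symmetric. If the sponsor prefers to keep the median of the paired differences, saying so explicitly removes most of the problem.

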9.4 Safety and Tolerability Assessments

9.4.1 Adverse events

Where changes in severity are recorded in the Case Report Form (CRF), each separate severity of the AE will be reported in the listings, only the most severe will be used in the summary tables. A pre-existing condition is defined as an AE that starts before the subject has provided written informed consent and is ongoing at consent. A non-treatment emergent AE is defined as an AE which starts after informed consent but prior to dosing. A treatment-emergent AE is defined as an AE which occurs postdose or which is present prior to dosing and becomes more severe postdose.

All AEs will be listed. Treatment-emergent AEs will be summarized by treatment, severity and relationship to the study drug. The frequency (the number of AEs, the number of subjects experiencing an AE and the percentage of subjects experiencing an AE) of treatment-emergent AEs will be summarized by treatment, Medical Dictionary for Regulatory Activities (MedDRA) version 20.0 system organ class and preferred term. The summary and frequency AE tables will be presented for all causalities and those considered related to the study drug. Any serious AEs will be tabulated.

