Treatment period: The subjects will be admitted to the clinical research unit (CRU) on the day before dosing (Day -1). Subjects will be discharged from CRU on Day 16 when all study procedures have been completed.

Follow-up period: Subjects will be discharged from the study approximately 10 days after the last dose of topiramate.

Number of subjects:

Approximately 30 subjects may be enrolled so that at least 21 complete the study.

Statistical Analysis:

Safety parameters that will be assessed include safety laboratory parameters, vital signs, neurological examination, Columbia Suicide Severity Rating Scale, and 12-lead electrocardiogram parameters. The parameters will be listed, and summarized using standard descriptive statistics, as appropriate.

Pharmacokinetic parameter estimates for lasmiditan, its metabolites, and topiramate will be calculated using standard noncompartmental methods of analysis. The parameters will be listed, and summarized using standard descriptive statistics, as appropriate.

Pharmacokinetic parameters will be evaluated to determine the impact of topiramate co-administration on the PK of a single dose of lasmiditan and its metabolites. Log-transformed C_{max} and area under the concentration versus time curve parameters will be evaluated in a linear mixed-effects model with fixed effects for treatment (lasmiditan co-administered with topiramate [Day 14; test treatment] versus lasmiditan alone [Day 1; reference treatment]), and a random effect for subject. The treatment differences will be back-transformed to present the ratios of geometric means and the corresponding 90% confidence interval (CI).

A similar analysis will be performed to determine the impact of co-administration of a single dose of lasmiditan on the steady-state PK of topiramate. The model will include the following treatments: topiramate co-administered with lasmiditan (Day 14; test treatment) versus topiramate alone (Day 13; reference treatment).

The t_{max} will be analyzed using the Wilcoxon signed rank test. Estimates of the median difference based on the observed medians, 90% CIs, and p-values from the Wilcoxon test will be calculated.

2. Schedule of Activities

Study Schedule Protocol H8H-MC-LAHT

	Screening	-1	Study Days															Discharge	Follow-up/ED	Comments
			1	2	3	4	5	6	7	8	9	10	11	12	13	14	15			
Procedure	-28 to -2 days prior to Day 1																Day 16	~10 days after last dose		
Informed Consent	X																			

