TEAE	treatment-emergent adverse event: Any untoward medical occurrence that emerges during a defined treatment period, having been absent pretreatment, or worsens relative to the pretreatment state, and does not necessarily have to have a causal relationship with this treatment
t_{max}	time of maximum observed drug concentration
ULN	upper limit of normal

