3. INTRODUCTION

This SAP has been developed after review of the Clinical Study Protocol (final version dated 03 August 2017 and Protocol Amendment (c) (final version dated 20 October 2017).

This SAP describes the planned analysis of the safety, tolerability and pharmacokinetic (PK) data from this study. A detailed description of the planned TFLs to be presented in the clinical study report (CSR) is provided in the accompanying TFL shell document.

The intent of this document is to provide guidance for the statistical and PK analyses of data. In general, the analyses are based on information from the protocol, unless they have been modified by agreement between Eli Lilly and Company and Covance Early Clinical (EC) Biometrics. A limited amount of information concerning this study (e.g., objectives, study design) is given to help the reader's interpretation. This SAP must be signed off prior to first subject administration for this study. When the SAP and TFL shells are agreed upon and finalized, they will serve as the template for this study's CSR.

This SAP supersedes the statistical considerations identified in the protocol; where considerations are substantially different, they will be so identified. If additional analyses are required to supplement the planned analyses described in this SAP, they may be performed and will be identified in the CSR. Any substantial deviations from this SAP will be agreed upon between Eli Lilly and Company and Covance EC Biometrics and identified in the CSR. Any minor deviations from the TFLs may not be documented in the CSR.

This SAP is written with consideration of the recommendations outlined in the International Council on Harmonisation (ICH) E9 Guideline entitled Guidance for Industry: Statistical Principles for Clinical Trials¹ and the ICH E3 Guideline entitled Guidance for Industry: Structure and Content of Clinical Study Reports².

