11. CHANGES FROM THE PROTOCOL SPECIFIED STATISTICAL ANALYSES

There were no changes from the protocol specified statistical analyses.

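### Does the lack of a stated end to each treatment's adverse-event window make the Day 14 versus Day 1 safety comparison unfair?

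*SAP*

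**What the plan says.** SAP 9.4.1 defines the event and how it is tabulated: "A treatment-emergent AE is defined as an AE which occurs postdose", or worsens after dosing, and "Treatment-emergent AEs will be summarized by treatment, severity and relationship to the study drug". Counts of events, counts of subjects and percentages are also given by treatment, system organ class and preferred term, for all causalities and again for related events. All AEs are listed.

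The treatments are the seven labels in SAP 6, the last being "50 mg topiramate + 200 mg lasmiditan". Each subject passes through five of them in a fixed order. There is no follow-up label. No passage in either document gives an end to a label's window or a rule for assigning an event among successive labels.

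Several passages bear on where the Day 14 window would end:

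- Protocol Appendix 1 defines a treatment-emergent AE as "Any untoward medical occurrence that emerges during a defined treatment period".
- The protocol synopsis separates a treatment period ("Subjects will be discharged from CRU on Day 16 when all study procedures have been completed") from a follow-up period ("Subjects will be discharged from the study approximately 10 days after the last dose of topiramate").
- SAP 3 states that "This SAP supersedes the statistical considerations identified in the protocol", and adds that substantial differences will be identified as such.
- SAP 11 records "There were no changes from the protocol specified statistical analyses".

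SAP 3 leaves the detailed description of the tables to a separate shell document. SAP 9.4.10 plans no inferential safety analysis.

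**The concern.** The primary endpoint is a summary of the numbers of treatment-emergent and serious AEs, and Protocol 5.4 intends each subject to serve as his or her own control for safety. A reader will therefore set the combination column (Day 14) beside the lasmiditan-alone column (Day 1) and take the difference as what topiramate adds.

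That reading needs windows of similar length. The lasmiditan-alone window closes when topiramate starts on Day 3. The SAP gives the Day 14 window no end and offers no follow-up label, so events up to the follow-up visit could fall to the combination by default. A window four to five times as long collects more background events. The combination could then look less well tolerated with no interaction at all.

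**Working it through.** The plan gives no AE rate, window length or power figure for safety, so there is no figure of its own to reproduce. The check has two parts: the window lengths, which come from the documents, and an illustration, whose rates are assumed.

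**Window lengths, if each AE goes to the most recent treatment**

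- Lasmiditan or placebo alone runs from the Day 1 morning dose to the first topiramate dose on Day 3. That is 2.0 days if the dose is given in the morning, as Protocol 7.1 says for each dosing day. It is 2.5 days if given in the evening, as the vital-signs comment in the Schedule of Activities implies. The two places disagree and must be reconciled; both values are used here.
- Day 14 treatments: 2 days if the window ends at Day 16 discharge, or about 10 if it runs to follow-up. The synopsis says approximately 10 days and Protocol 5.1 at least 10, so 10 is not a ceiling.
- Ratio of the Day 14 window to the Day 1 window: from 2/2.5 = 0.8 to 10/2 = 5.

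**Illustration**

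Let p be the acute AE risk from lasmiditan, h the background rate per subject-day and t the window in days. Assume no interaction and no effect of topiramate.

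- Lasmiditan arm: share with an AE = 1 - (1 - p)·exp(-h·t)
- Placebo arm: share with an AE = 1 - exp(-h·t)
- Difference = p·exp(-h·t)

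If only a share c of the events after Day 16 is captured, the effective Day 14 window is t = 2 + 8c. With p = 0.40 and h = 0.02:

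| t (days) | Case | exp(-0.02t) | Placebo | Lasmiditan | Difference (points) |
|---|---|---|---|---|---|
| 2 | Day 1, or Day 14 to Day 16 | 0.9608 | 3.9% | 42.4% | 38.4 |
| 2.5 | Day 1, evening start | 0.9512 | 4.9% | 42.9% | 38.0 |
| 4 | Day 14, c = 0.25 | 0.9231 | 7.7% | 44.6% | 36.9 |
| 6 | Day 14, c = 0.5 | 0.8869 | 11.3% | 46.8% | 35.5 |
| 10 | Day 14, c = 1 | 0.8187 | 18.1% | 50.9% | 32.7 |

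**Apparent Day 14 excess in the lasmiditan arm**

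- Window ends at Day 16: 0.0 points (against 2 days) or -0.6 (against 2.5 days).
- 25% to 50% capture: 2.3 to 4.4 points against 2 days, or 1.7 to 3.9 against 2.5 days. With 20 lasmiditan subjects (2:1 of 30), 2.3 to 4.4 points is 0.45 to 0.9 of a subject.
- Full capture: 8.5 or 7.9 points, that is 1.7 or 1.6 subjects.
- Full capture over p = 0.2 to 0.6 and h = 0.01 to 0.05: 2.8 to 23.9 points. The top value needs 1 - exp(-0.05 × 10) = 39% of healthy subjects to have a background AE in 10 days.

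**What the placebo arm shows**

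In this model the lasmiditan arm's rise equals (1 - p) times the placebo arm's rise, for any rate and any pair of windows. At full capture the placebo arm rises by 18.1 - 3.9 = 14.2 points (13.2 against 2.5 days), and 0.6 × 14.2 = 8.5. The false excess therefore never appears in the lasmiditan arm without a larger expected rise under placebo.

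On expected event counts the effect cancels: each arm gains 0.02 × (10 - 2) = 0.16 background events per subject. On percentages the lasmiditan-placebo difference falls from 38.4 to 32.7 points, which is the opposite of a false interaction.

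**The case for a change.** The best case for a change is that this is the primary endpoint, the remedy costs a sentence or two and one table, and a window chosen after the data are seen is what a SAP exists to prevent. AEs may well be collected to follow-up: Protocol 9.2.1 releases investigators from actively seeking events only once a subject has completed or discontinued, and Protocol 8 requires AE and follow-up procedures after early discontinuation. The two drugs also share expected AEs (dizziness, somnolence, paresthesia, nausea, fatigue). An event that starts on topiramate and worsens after the Day 14 dose has no stated home, because only its most severe grade enters the summaries.

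The silence is real, and so is the possibility of a 10-day window. The harm is less clear. The protocol's own definition ties a treatment-emergent AE to a defined treatment period, the synopsis closes that period at Day 16, and SAP 11 declares no departure from the protocol. That favours the reading under which the windows are about equal, though it does not exclude the other.

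An added table limited to 0-48 hours after each lasmiditan or placebo dose would gain little. By Day 14 subjects have taken topiramate since Day 3, so Day 14 versus Day 1 would still mix topiramate's own overlapping AEs, and time, with any interaction. The placebo arm has to do that separation whatever the window. With about 10 placebo subjects it does so imprecisely, and a table with equal windows would not cure that.

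**Conclusion.** No change to the plan is needed. The documents leave out a detail; they do not prescribe an analysis that gives a wrong answer. Whoever programs the tables must choose an assignment rule, and the natural choices (most recent treatment at onset, with events after discharge shown as follow-up) give windows of about 2 days against 2 to 2.5. The shells may already say so.

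If the Day 14 window did run to follow-up, the raw Day 14 versus Day 1 percentages would carry extra background events in both arms: 7.9 to 8.5 points for lasmiditan and 13.2 to 14.2 for placebo at the assumed central rates with full capture. Lasmiditan versus placebo within each period stays unbiased, although the size of the percentage difference depends on window length. The AE listings and the related-AE tables let a reader check what the extra events are, and no safety test or error rate depends on the choice.

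This rests on the same rule being applied to both arms, which share dosing days and topiramate schedule, and on a constant background rate. The rates are assumptions, and the AE review row of the Schedule of Activities does not settle, in the copy available, whether events are reviewed at follow-up. The disagreement over the time of the Day 3 topiramate dose needs reconciling in its own right, but here it moves one window by only half a day.
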